9.4 Follow-up

Patient medical records will be reviewed through 90 days post-procedure for assessment of adverse events and patency (including reintervention or abandonment of the AV dialysis access site). Adverse event reporting will be limited to those events listed in Section 9.6: Adverse Events. Events occurring after 90 days post-procedure will not be collected. Clinical success will be determined, and is defined as resumption of successful dialysis for at least one session. The follow-up requirements are summarized in Table 9.4-1.

Table 9.4-1. Follow-up requirements

90 Day Follow-up	
Timing	Through 90 days following the study procedure
Type	Chart Review
	Record if patient received at least one successful hemodialysis treatment after the study procedure
	Record adverse events (including, but not limited to, reintervention or abandonment of the study access circuit; refer to section 9.6: Adverse events for a list of reportable events)

9.5 Reintervention

Patients requiring a reintervention within the study lesion may be treated in accordance with the institution's standard of care. Treatment information will be recorded on the appropriate eCRF.

9.6 Adverse Events

The following adverse events, occurring after the point of enrollment until the last day of patient participation, are to be reported to the sponsor using the appropriate eCRF:

- Events with potential relationship to the study device or study procedure
- Serious Adverse Events
- Restenosis or occlusion resulting in a reintervention or abandonment of AV dialysis access circuit

Information regarding occurrence of adverse events (including onset date, end date, date of awareness, event description, treatment, and whether the device or procedure contributed to the event) will be captured throughout the study and recorded on the appropriate eCRF.

Sites are responsible for following their normal reporting process (e.g., to manufacturer, to regulatory authority) for commercially available devices.

The sponsor is responsible for reporting events to the reviewing IRB(s) and principal investigator(s) as required according to applicable regulations/standards/policies.

10.0 Participation Endpoints of the Study

A patient's participation in the study will end after any of the following:

- Patient withdrawal (patient- or investigator-initiated)
- Medical records determined to be unobtainable for chart review
- Early termination of the study
- Patient death
- Completion of 90-Day chart review

After a patient exits the study for any reason (e.g., withdrawal, records determined to be unobtainable, study closure, or study completion), no additional data will be collected. Information up to the date of the participation endpoint will be provided to the Sponsor during the 90-Day chart review.

10.1 Patient Withdrawal

A patient may decide to withdraw from the study at any time either before or after undergoing the study procedure without prejudice or loss of care. The principal investigator may also decide to withdraw the patient from the study at any time based on medical judgment. If a patient is withdrawn, a medical chart review will be conducted through and including the date of withdrawal. In all instances of withdrawal, data collected up to the time of patient withdrawal will be submitted and will include the reason why the patient has been withdrawn from the study. Any data collected on the patient up to the point of withdrawal may be used in the study.

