11.4 Missing Data

For the primary endpoint, minimal or no missing data is expected. Missing primary outcome will be assumed missing at random and excluded for analyses. However, if more than 5% of primary endpoint is missing, multiple imputation technique will be applied followed by sensitivity analyses. All the other measurements will be analyzed accordingly with all available data using a complete case approach.

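### Investigator-initiated withdrawal after the procedure stops the 90-day chart review, so later patency and adverse event data can be lost in a way related to outcome and arm

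*Combined protocol and SAP*

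**What the plan says.** Section 10.1 (Patient Withdrawal) gives the investigator an open right: "The principal investigator may also decide to withdraw the patient from the study at any time based on medical judgment". It is not limited to the time before the procedure, and no permitted reasons are listed. The consequence for data follows: "If a patient is withdrawn, a medical chart review will be conducted through and including the date of withdrawal". The data submitted "will include the reason why the patient has been withdrawn from the study".

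Section 10.0 (Participation Endpoints of the Study) names withdrawal by patient or by investigator as one event that ends participation, and treats the two alike. "After a patient exits the study for any reason", it says, "no additional data will be collected". Section 9.6 closes adverse event reporting on the last day of participation, so withdrawal closes that window too.

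Section 9.4 describes follow-up as a review of the medical record through day 90. Section 10.2 keeps every treated patient in follow-up for 90 days if a site or the study closes.

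For analysis, Section 11.4 reserves multiple imputation and sensitivity analyses for the primary endpoint. For the rest: "All the other measurements will be analyzed accordingly with all available data using a complete case approach". Section 11.3.3 adds Kaplan-Meier or Cox methods for the additional measures if data are censored.

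**The concern.** In a trial of continuing treatment, withdrawal on medical judgment protects the patient by taking them off study treatment. Here the study treatment is one procedure, reintervention follows the institution's standard of care (Section 9.5), and no study visit is scheduled afterwards. Once the procedure is over, an investigator's withdrawal therefore ends data collection and nothing else in the study.

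The decision rests with someone who can be expected to know the arm. Section 7.4 relies on randomization, stratification, a site cap and uniform definitions. It describes no blinding, and the operator handles the assigned balloon. If withdrawals are related to how the access is doing, and differ between arms, the 90-day comparison is distorted.

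The exposed outcomes are reintervention/patency (listed among the safety measures in Section 7.5.2), and primary patency, clinical success and adverse events (Section 7.5.3). In each case only what happens after the withdrawal date is exposed.

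**Working it through.** **What the text does at each kind of exit after the procedure**

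| Exit | Later data under the plan |
|---|---|
| Patient withdraws | None after that date (10.0, 10.1) |
| Investigator withdraws the patient | None after that date (10.0, 10.1) |
| Site or study closure | 10.2: followed for 90 days; 10.0: no additional data |

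The first row reflects the patient's choice. The second has no equivalent reason once the procedure is done. The third is an internal contradiction. Section 10.0 also says that information up to exit is supplied during the 90-day chart review, so the chart is opened in any case and reading stops at the withdrawal date.

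**Size, as an illustration only.** The plan states no withdrawal rate, so it has no figure of its own to reproduce.

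Inputs:
- About 100 patients per group (Section 11.1).
- Loss of patency at 90 days of 100 − 62.0 = 38%, from the Kaplan-Meier estimate in the earlier single-arm study (Section 5.0). It is assumed to be the true rate in both arms.
- *k* patients withdrawn, in the Enforcer arm only, each before a loss that would have occurred. This is an assumption, and *k* is shown as a range.

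Complete-case loss in the Enforcer arm = (38 − *k*) / (100 − *k*).

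| *k* of 100 | Observed loss | Shift from 38% | Share of the 38 losses removed |
|---|---|---|---|
| 1 | 37/99 = 37.4% | 0.6 points | 1/38 = 2.6% |
| 2 | 36/98 = 36.7% | 1.3 points | 2/38 = 5.3% |
| 5 | 33/95 = 34.7% | 3.3 points | 5/38 = 13.2% |

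**Equal withdrawal in both arms.** With *k* = 5 in each arm and equal true rates, both arms show 34.7% and the difference stays at zero. Both rates look too low, but the comparison is not shifted. If the withdrawals were in the conventional arm only, the same shifts would count against Enforcer.

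**Would the planned analysis correct it?** Complete-case analysis drops the withdrawn patients and treats those left as representative. Kaplan-Meier and Cox censoring assume that a censored patient has the same later risk as comparable patients still under observation. In the illustration every withdrawn patient was going to lose patency, so both assumptions fail.

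**The case against.** The case against is substantial, and much of it stands.

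- **The prompting event is kept.** Chart review runs through and including the withdrawal date, the reason is submitted, and data to that point may be used. A reader might infer that the complication or failing access behind a withdrawal disappears, or that the rule removes exactly the patients with events. The documents do not support that: an event up to and including that date is captured, and nothing says why patients would be withdrawn. Only later events are lost.
- **There is oversight.** Section 14.0 provides central review of data completeness, and Appendix C (2.2) has the monitor check that reasons for non-completion are documented. This makes selective withdrawal visible but does not recover the data.
- **The occasion may be rare.** With nothing left to stop, an investigator has little reason to withdraw a treated patient, and the clause also serves withdrawal before the procedure. The text shows an opportunity for bias, not that bias will occur.
- **The illustration is one-sided by construction.** It puts all withdrawals in one arm and makes every withdrawn patient a future loss.
- **The margin is not tied to patency.** A reader might set 3.3 points against the 10% non-inferiority margin and call it a third of the margin. Section 11.3.2 applies that margin to a safety claim that it does not define. Section 7.5.2 groups rupture, tears and reintervention/patency together, and Section 7.5.3 lists 90-day primary patency separately. The ratio cannot be asserted from the text.
- **The patient's own right must be respected.** After the procedure, chart review is all that remains of the study. Continuing it against a patient's withdrawal would empty that right, and it cannot be completed where records are unobtainable.

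What survives is narrower: the rule for investigator-initiated withdrawal after the procedure serves no stated purpose, and the analysis plan has no remedy for what it can lose.

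**Conclusion.** The point holds for investigator-initiated withdrawal after the procedure, and for outcomes after the withdrawal date. As written, an investigator for whom no blinding is described can end collection of a treated patient's 90-day data when no study treatment or visit remains.

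The primary endpoint is observed at the procedure (Section 7.5.1) and is not exposed, nor are the other procedural outcomes. A reader might infer that the main comparison or the sample size is at risk; neither is.

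The size is unknown because no withdrawal rate is given. Under the one-arm assumption and 38% true loss, 1 to 5 such withdrawals per 100 shift the observed loss by about 0.6 to 3.3 points; balanced withdrawal with equal true rates shifts the difference by nothing. The change is worth making because it is cheap and Section 10.2 already accepts the principle for closures, not because a large bias has been shown.

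**What to change.** In Sections 10.0 and 10.1, state that after the study procedure an investigator-initiated withdrawal does not end data collection. The 90-day chart review is then completed for patency, reintervention, abandonment, adverse events and death, where records are obtainable and unless the patient withdraws consent. Leave patient-initiated withdrawal as written.

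Align the adverse event window in Section 9.6, which now closes on the last day of participation. Reconcile Section 10.0, under which early termination or study closure ends data collection, with Section 10.2, which follows treated patients for 90 days after closure.

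The cost is a few more charts read to day 90 and a line of consent wording (the consent form was not available to check). No visit, procedure, sample size, error rate or power changes.

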10.2 Early Termination or Suspension of the Clinical Study

Any decision to suspend enrollment or terminate the clinical study either completely or at multiple clinical sites will be made by the sponsor. The sponsor or the IRB may decide to suspend enrollment or terminate the study at an individual clinical site. Reasons for early termination or suspension of a study (or at one or more sites) may be due to safety concerns, effectiveness concerns, ethical concerns, alterations in accepted clinical practice, clinical site performance, or organizational issues. In the event of clinical site or study closure, all patients who have received the study treatment will be followed for 90 days following the study procedure.

The principal investigator-required notifications/reports are described in Table 10.2-1. The reports will be provided as required by the study plan, IRB policies, or local regulations, whichever is more stringent.

Table 10.2-1. Early Termination or Suspension Reports

Report	To	Timeframe to submit report (upon awareness)
IRB initiated suspension or early termination	Sponsor Patient	Within 5 working days
Sponsor initiated suspension or early termination	IRB Patient	Within 5 working days

The sponsor is responsible for reporting early termination or suspension of the study to reviewing IRB(s) and principal investigator(s) as required according to applicable regulations/standards.

11.0 Statistical Considerations

11.1 Sample Size

The expected rates of adjunctive therapy for the Enforcer balloon and conventional angioplasty groups were assumed to be 5% and 15%, respectively. A sample size of at least 250 total lesions (125 lesions per group) is required to detect a 10% difference in the rate of adjunctive therapy with a power of 80% and a type I error of 0.05. Prior experience suggests that 40% of patients, on average, would also have a second lesion treated. Therefore the study will enroll approximately 200 patients (approximately 100 patients per group) and enrollment will continue until at least 250 lesions are treated. Procedural outcomes are unlikely to depend on the connectivity between lesions within an AV dialysis access circuit or the patient-level factors which affect longer-term outcomes, and therefore lesions were assumed to be independent for the purposes of the sample size calculation.

Up to 10 clinical sites will be included in the study, and the maximum enrollment per clinical site will be no more than 80 patients or 40% of the total enrollment. There is no minimum enrollment threshold. Patients that withdraw from the study will not be replaced.

11.2 Randomization

Once patient eligibility is confirmed, patients will be randomized into either the Enforcer balloon or conventional angioplasty group prior to treatment in a 1:1 ratio at each study site. Randomization will be first stratified by the number of lesions requiring treatment (single lesion or two lesions) and type of AV access circuit (fistula or graft). Using restricted randomization maximizes the balance of treatment allocations within stratum and vice versa. Randomization codes will be maintained by the Sponsor.

11.3 Analyses

11.3.1 Primary endpoint analysis

The study is intended to compare the necessity of adjunctive therapies for lesions treated with the study device (Enforcer balloon) compared to those treated with the control device (conventional angioplasty balloon inflated to standard pressures). The null (H_0) and alternative (H_A) hypotheses are expressed as follows:

$H_0: AT_{EB} \geq AT_{CA}$

$H_A: AT_{EB} < AT_{CA}$

where AT_{EB} is the rate of adjunctive therapies in the Enforcer balloon group and AT_{CA} is the rate of adjunctive therapies in the conventional angioplasty balloon group.

The rates of adjunctive therapies will be compared between the two treatment groups with a one-sided Z-test. A p-value $< .05$ will be used to claim statistical significance. If the number of patients within each strata are sufficiently large, the association of stratification factors and treatment will be assessed. Crude and adjusted, if applied, differences in rate of adjunctive therapies between the two treatment groups and 95% confidence intervals will be reported.

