7.4.1 Randomization

Once baseline angiography is complete and patient eligibility is confirmed, patients will be randomized into either the Enforcer balloon or conventional angioplasty group prior to treatment. At each study site, patients will be stratified for randomization based on the number of lesions requiring treatment (single lesion or two lesions) and type of AV access circuit (fistula or graft), then randomized to one of the treatment groups in a 1:1 ratio.

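### Patients are randomised but the primary Z-test counts lesions, with no allowance for two lesions in one patient; positive residual correlation would make the standard error modestly too small

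*Combined protocol and SAP*

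**What the plan says.** **Randomisation is by patient.** Section 11.2: "patients will be randomized into either the Enforcer balloon or conventional angioplasty group prior to treatment in a 1:1 ratio at each study site". Section 7.4.1 adds the strata: "At each study site, patients will be stratified for randomization based on the number of lesions requiring treatment", together with access type (fistula or graft).

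**The endpoint is by lesion.** Section 7.5.1 defines the primary endpoint as a percentage of lesions. Section 9.1 allows up to two treated lesions per patient. Section 11.1 states: "Prior experience suggests that 40% of patients, on average, would also have a second lesion treated". Recruitment is also governed by lesions: "enrollment will continue until at least 250 lesions are treated".

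**The analysis is an ordinary comparison of rates.** Section 11.3.1: "The rates of adjunctive therapies will be compared between the two treatment groups with a one-sided Z-test". It continues: "Crude and adjusted, if applied, differences in rate of adjunctive therapies between the two treatment groups and 95% confidence intervals will be reported". The optional adjustment concerns the stratification factors. Section 11.5 leaves site out of the primary analysis. Nothing in Sections 11.3 to 11.5 provides a clustered or robust variance, a mixed model, a patient-level test or a sensitivity analysis for within-patient dependence.

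**Independence is assumed for planning only.** Section 11.1 reasons: "Procedural outcomes are unlikely to depend on the connectivity between lesions within an AV dialysis access circuit", nor on patient factors that drive longer-term results. It concludes: "therefore lesions were assumed to be independent for the purposes of the sample size calculation". No data are given in support.

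**The concern.** A two-sample Z-test on lesion counts treats every lesion as a separately randomised unit. On the plan's own 40% figure, 0.8/1.4 = 57% of the analysed lesions share a patient with another analysed lesion.

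The documents point both ways on correlation. Table 7.6-1 measures use of a device after the initial balloon, and Table 9.3-1 ties adjunctive procedures to residual stenosis below 30%; both are lesion-level. But Table 9.3-1 also allows adjunctive treatment when the physician judges it best for the patient. Appendix D links adjunctive therapy to clinical success, which is resumption of dialysis and so belongs to the patient. Both lesions share one access circuit. Positive correlation is therefore plausible but not established.

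The kind of correlation matters. What arises only from site or access type is balanced by the stratified randomisation, and leaving it out of the test makes the Z-test conservative. Only positive correlation beyond site and strata shrinks the standard error wrongly. If it is present, the single primary success claim, tested one-sided at 0.05, rests on a p-value that is too small and an interval that is too narrow.

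**Working it through.** **Inputs from Section 11.1:** 5% versus 15%; 125 lesions per group; 80% power; type I error 0.05; 40% of patients with a second lesion; about 200 patients. From Section 11.3.1: one-sided test at 0.05. **Assumed:** the residual within-patient ICC, ρ = 0.1, 0.3, 0.5, with 1 as the ceiling.

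**The plan's 250 lesions.** With independent lesions, the one-sided pooled Z-test needs 222 lesions and has 84.2% power at 250. The stated 250 is matched approximately by the one-sided unpooled formula with continuity correction (256), or by a one-sided Fisher test at 125 per group (power 79.8%). The two-sided variants tried do not match it (pooled power 75.3% at 250).

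**Two lesion mixes.** With 40% two-lesion patients, 200 patients give 200 × 1.4 = 280 lesions, and 250 lesions come from 250/1.4 ≈ 179 patients. Exactly 250 lesions from 200 patients means a 25% share.

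**Design effect.** DE = 1 + (Σm²/Σm − 1)ρ, where m is lesions per patient.
- 40% share: (0.6×1 + 0.4×4)/1.4 − 1 = 2.2/1.4 − 1 = 0.571
- 25% share: (0.75×1 + 0.25×4)/1.25 − 1 = 1.75/1.25 − 1 = 0.400

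True SE / planned SE = √DE. Actual one-sided alpha = 1 − Φ(1.645/√DE). Coverage of the 95% interval = 2Φ(1.96/√DE) − 1.

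| Share | ρ | DE | SE ratio | One-sided alpha | 95% CI coverage |
|---|---|---|---|---|---|
| 40% | 0.1 | 1.057 | 1.03 | 5.5% | 94.3% |
| 40% | 0.3 | 1.171 | 1.08 | 6.4% | 93.0% |
| 40% | 0.5 | 1.286 | 1.13 | 7.3% | 91.6% |
| 40% | 1 | 1.571 | 1.25 | 9.5% | 88.2% |
| 25% | 0.1 | 1.040 | 1.02 | 5.3% | 94.5% |
| 25% | 0.3 | 1.120 | 1.06 | 6.0% | 93.6% |
| 25% | 0.5 | 1.200 | 1.10 | 6.7% | 92.6% |
| 25% | 1 | 1.400 | 1.18 | 8.2% | 90.2% |

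**What ρ means.** At a 10% event rate, P(second lesion | first lesion) = 0.10 + 0.90ρ = 19%, 37%, 55% for ρ = 0.1, 0.3, 0.5.

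**Benchmark.** With independent lesions, the exact size of the pooled one-sided Z-test at 125 per arm is 5.2% at a 10% rate and 5.6% at 5%. The inflation at ρ = 0.1 is no larger than this ordinary approximation error.

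**Null simulation** (40,000 runs per case, Monte Carlo SE about 0.1 point). Assumed: 200 patients, 10 sites of 20, blocks of 2 within site × lesion number × access type, 30% grafts, 10% event rate.

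| Share | Patient ICC | Site-by-access ICC | Planned Z-test | Patient-clustered test |
|---|---|---|---|---|
| 40% | 0 / 0.1 / 0.3 / 0.5 | 0 | 4.95 / 5.68 / 6.27 / 7.30% | 5.02 / 5.25 / 4.94 / 5.06% |
| 25% | 0 / 0.1 / 0.3 / 0.5 | 0 | 4.86 / 5.29 / 6.09 / 6.84% | 4.98 / 5.02 / 5.22 / 5.25% |
| 40% | 0 / 0.1 / 0.3 | 0.1 | 4.50 / 4.73 / 5.99% | 4.21 / 3.99 / 4.38% |
| 25% | 0 / 0.1 / 0.3 | 0.1 | 4.26 / 4.74 / 5.46% | 4.04 / 4.24 / 4.36% |

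Clustered 95% interval coverage was 94.6 to 95.0% in the eight cases without the site-by-access component.

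**Power with a valid variance** (5% versus 15%, one-sided 0.05, pooled null SE, SEs scaled by √DE), ρ = 0.1 / 0.3 / 0.5:
- 250 lesions, 200 patients (25% share): 83 / 80 / 78%
- 250 lesions, about 179 patients (40% share): 82 / 79 / 75%
- 280 lesions, 200 patients (40% share): 86 / 83 / 80%

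**The case against.** The sponsor saw the issue and gave a clinical reason. That reason concerns the outcome itself, so it could be carried over to the test. The harm depends on an ICC that the documents do not supply, and nothing in them supports a value as high as 0.5. At a patient ICC of 0.1, a site-by-access ICC of 0.1 brings the planned test to 4.7%, below nominal. In that setting the clustered test, at 4.0 to 4.2% for patient ICC 0 and 0.1, is further from 5% than the planned test.

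Nor is the clustered test exact. Without a site effect its size was 5.3 to 5.4% at a 5% null rate and 5.7 to 6.0% at 3% in a separate simulation, though still closer to 5% than the planned test there. Recruitment could also stop at about 179 patients, where power is 79% at ICC 0.3 and 75% at 0.5. On this view, a clustered sensitivity analysis beside the Z-test would be enough.

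These points stand as limits on size. The direction of the net error is not certain at small ICC, and ICC 0.5 and 1 are boundary cases. They do not remove the mismatch. Section 11.1 confines the independence assumption to the sample size and offers no data, and the site offset is not guaranteed: at patient ICC 0.3 the planned test still runs at 5.5 to 6.0%. The clustered test errs on the conservative side when site correlation is present, whereas the planned test can err in the sponsor's favour.

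**Conclusion.** The concern holds as a conditional statement. The randomised unit and the analysed unit differ, and the primary test and interval have no variance for that. If positive correlation beyond site and strata exists, the planned standard error is too small: the true value is 2 to 13% larger for ICC 0.1 to 0.5. One-sided alpha is then 5.3 to 7.3%, and interval coverage 94.5 to 91.6%. At ICC 0.1 the effect is negligible in practice; at 0.3 it is about 1 to 1.4 points of alpha when there is no site or access-type correlation, and less when there is.

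These figures rest on an assumed ICC, a two-lesion share of 25 to 40%, and, for the simulations, the site and graft mix listed above. Power is not the main problem, since 250 lesions exceed the 222 that the planned test needs under independence. The point should be fixed because it affects the only primary success claim and is cheap to remove; it is not a fatal flaw.

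**What to change.** In Section 11.3.1, base the one-sided test and the 95% interval for the lesion-level risk difference on a patient-clustered variance. Either GEE with robust variance or a ratio-estimator Z-test with patient as the unit would serve. Keep the ordinary Z-test as a sensitivity analysis. Use the same variance for any secondary endpoint that turns out to be analysed per lesion; Section 11.3.2 does not say which are.

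**Cost.** SAP wording and a few lines of code. The p-value may be slightly less favourable, and the test is mildly conservative (4.0 to 4.4% in the simulation) if site or access-type correlation is present. No enrolment beyond the planned 200 patients is needed: power is about 80% or more up to ICC 0.3 at 250 lesions, and up to ICC 0.5 at 280. Stopping at 250 lesions from about 179 patients would give 79% at ICC 0.3 and 75% at 0.5, so the planned 200 patients should be kept. If lesions are in fact independent and site correlation is small, the two analyses will nearly agree and little is lost.

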7.0 Design of the Clinical Study

7.1 Design of the Clinical Study

This multicenter, stratified, randomized, controlled clinical study will evaluate the performance of the Enforcer balloon compared to commercially available conventional balloons (defined as less than 25 atm rated burst pressure) in the treatment of stenoses of the AV dialysis access circuit.

This study will enroll approximately 200 patients at up to 10 clinical sites. Enrollment will end when it is determined a minimum of 250 lesions have been treated.

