9.2 Point of Enrollment

Patients are considered enrolled in the study once the balloon catheter is first introduced into the patient's body.

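### Does Section 11 need to name its analysis set, and say how lesions of randomised but untreated patients count under the 5% missing-data rule?

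*Combined protocol and SAP*

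**What the plan says.** The plan counts patients or lesions at three points.

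- **Randomised.** Section 7.4.1 stratifies patients, "then randomized to one of the treatment groups in a 1:1 ratio", before treatment. Section 11.2 repeats this and names the two groups, Enforcer balloon and conventional angioplasty.
- **Enrolled.** Section 9.2: "Patients are considered enrolled in the study once the balloon catheter is first introduced into the patient's body". This comes after randomisation.
- **Treated.** Section 7.1: "Enrollment will end when it is determined a minimum of 250 lesions have been treated". Section 11.1 agrees: "enrollment will continue until at least 250 lesions are treated". It adds: "Patients that withdraw from the study will not be replaced".

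For the primary analysis, Section 11.3.1 first describes its purpose as being to "compare the necessity of adjunctive therapies for lesions treated with the study device (Enforcer balloon) compared to those treated with the control device". It then defines one adjunctive-therapy rate for the Enforcer group and one for the conventional group, states the hypotheses on those rates, and gives the test: "The rates of adjunctive therapies will be compared between the two treatment groups with a one-sided Z-test".

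Section 11.4 expects little or no missing primary data. It excludes missing outcomes under a missing-at-random assumption, with one exception: "if more than 5% of primary endpoint is missing, multiple imputation technique will be applied followed by sensitivity analyses".

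Section 7.5.1 defines the endpoint per lesion, after initial treatment with one of the study balloons.

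**The concern.** Nowhere does the plan say intention-to-treat, as-treated or per-protocol, and it does not say in which arm to count a lesion treated first with the non-assigned balloon. The purpose sentence of 11.3.1 speaks of lesions by the device they were treated with, which could be taken as analysis by device used. In an open-label device trial, regrouping by device used can bias the comparison if operators switch balloons on harder lesions.

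The 5% rule in 11.4 has a similar gap. Section 10.1 allows withdrawal before the procedure. Table 9.1-1 confirms that a guidewire crosses the lesion, not that a balloon does. A study lesion can therefore belong to a randomised patient and have no initial balloon treatment. If only treated lesions count, that loss is 0% by construction and the imputation step never runs for it, however one-sided it is. If all study lesions of randomised patients count, the step can run. Continuing recruitment to 250 treated lesions also seems to replace such patients, despite the no-replacement sentence.

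At stake would be the type I error of the primary test and a choice of denominator left open until the data are seen.

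**Working it through.** **1. Which groups are compared?** Section 7.4.1 uses the term treatment groups for the arms patients are randomised to. Section 11.2 randomises patients into the Enforcer and conventional groups. Section 11.3.1 defines its rates on groups with those names and tests between them. Table 9.3-1 has angioplasty follow the randomisation. The only text pointing elsewhere is the purpose sentence of 11.3.1, which sets no rule of analysis. Assigned arm is the natural reading.

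**2. Is the replacement wording contradictory?** Under 9.2 a patient who never receives a balloon is not enrolled, so recruitment simply continues. A patient who withdraws after treatment has already contributed a treated lesion and is not replaced. The two statements in 11.1 can stand together.

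**3. The plan's own figure.** Inputs from 11.1 and 11.3.1: rates 5% and 15%, 125 lesions per arm, one-sided 0.05, independent lesions. With pooled variance under the null (mean rate 0.10):

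power = Φ{[0.10 − 1.645·√(2·0.10·0.90/125)] / √[(0.05·0.95 + 0.15·0.85)/125]} = Φ{(0.10 − 0.0624)/0.0374} = Φ(1.004) = 84.2%.

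Exact enumeration of the same test gives 86.2%. A one-sided Fisher or continuity-corrected test gives 79.8%, which matches the stated 80%.

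**4. Crossover (assumed; the plan gives no rate).** Both arms have a true rate of 10% with 125 lesions each, and 6 Enforcer-assigned lesions (6/125 = 4.8%) are treated first with a conventional balloon. In each arm 6 lesions have risk r and 119 have risk (12.5 − 6r)/119, so the arm mean stays at 10%. Exact one-sided type I error of the pooled Z-test:

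| r | By assigned arm | By device used |
|---|---|---|
| 10% | 5.2% | 5.1% |
| 20% | 5.1% | 8.3% |
| 30% | 5.0% | 12.7% |

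The reverse switch at r = 30%, analysed by device used, gives 1.5%. The distortion needs one-way switching, lesions well above average risk, and the less likely reading, all together.

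**5. Loss before treatment (assumed).** The expected counts are 0.05 × 125 = 6.25 and 0.15 × 125 = 18.75, rounded to 6 and 19. The test is z = (p_C − p_E)/√[p̄(1 − p̄)(1/n_E + 1/n_C)].

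- 6/125 against 19/125: z = (0.152 − 0.048)/0.03795 = 2.741, p = 0.003.
- 6 lost Enforcer lesions added, 5 of them events: 11/131 against 19/125, z = 1.692, p = 0.045.
- 6 lost, all 6 events: 12/131 against 19/125, z = 1.481, p = 0.069.
- 13 lost, 5 events: 11/138 against 19/125, z = 1.842, p = 0.033.
- 13 lost, 6 events: 12/138 against 19/125, z = 1.634, p = 0.051.

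No control lesion is lost in any of these. The last case needs an event rate of 6/13 = 46% in the lost lesions, against 4.8% in the treated ones.

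**6. When would the denominator matter?** With 250 treated lesions, 13 untreated give 13/263 = 4.9% and 14 give 14/264 = 5.3%. Fourteen lesions are 14/1.4 = 10 patients at the 40% second-lesion rate in 11.1, or 14/1.25 = 11.2 at 250 lesions in 200 patients. The two readings of 11.4 diverge only if about ten or eleven patients are lost between randomisation and the balloon. Angiography, eligibility and guidewire crossing are all settled before randomisation.

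**The case for a change.** The case for a change is that pre-specification should close off choices once data are in hand, and the plan leaves two open. Withdrawal before the procedure is expressly allowed, a balloon can fail where a wire passed, and Section 12.0 bars only unapproved deviations, with an exception for emergencies. A denominator that counts treated lesions alone would disable the 5% safeguard for this kind of loss. The cost would be two sentences, a table by arm and one sensitivity analysis.

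The silence on both points stands, and the second is the clearer of the two. What does not follow is that the plan's rule is wrong or that the added text would improve the inference. Because 7.5.1 defines the endpoint after initial balloon treatment, a lesion without that treatment may as well lie outside the endpoint as be missing. Calling it missing is a choice of estimand. For a balloon that cannot cross, that label would, at or below 5%, send a plausibly device-related failure into the missing-at-random exclusion of 11.4. A sensitivity analysis run whatever the missing share would override the trigger the plan chose.

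Analysis by assigned arm also loses power under crossover. Exact power at 125 per arm is 86.2% with none, 82.0% at 3% two-way and 78.8% at 5%; the normal approximation gives 84.2%, 80.0% and 76.9%. That is the ordinary price of preserving randomisation and needs no new sample size at low crossover.

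**Conclusion.** No change follows. Read together, 7.4.1, 11.2 and 11.3.1 point to comparison of the randomised groups, and on that reading the primary test keeps its size: 5.0% to 5.2% in the crossover scenario examined. The larger errors belong to a reading the text does not favour, combined with selective one-way switching. The denominator in 11.4 is unstated, but it changes the handling only after about ten or eleven patients are lost in a short window, and even then the planned result is overturned only by extreme, one-sided event rates among the lost lesions. An analyst would ordinarily report untreated and crossover patients by arm with reasons, and 10.1 already requires the reason for each withdrawal.

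This rests on assumed loss and crossover rates, since the plan gives none, and on independent lesions as in 11.1. A sentence confirming each point would do no harm, but the plan gives a sound result without it.
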